6.2.3 In-person follow-up procedure at 9 and 15 months (for randomized subjects)

- Assess for adverse events including MI, unstable angina, stroke, and bleeding.
- Review concomitant medications with subject
- Collect pill bottles, perform study medication accountability, and remind subject about importance of study drug compliance.
- Dispense study medication for next 6 months for those patients still taking study provided medications at the 9-month in-person visit. Patients who have permanently stopped study-provided medications prior to the 9-month in-person visit will continue to be followed but will not be provided additional study medication.
- Instruct the subject to notify the investigator of any occurrence of any adverse events.
- Schedule next clinic visit at 15 months
- Instruct patients to return all study-provided medication at next in-person clinic visit (only pertains to 9-month in-person clinic visit)

6.2.4 Phone-call follow-up contact at 1, 4 and 18 months post enrollment

- Assess for adverse events including MI, unstable angina, stroke, and bleeding.
- Review all medications and compliance with subject
- Instruct the subject to notify the investigator of any occurrence of adverse events

6.3 Efficacy and safety variables

The study site research personnel will collect data from the subjects during the follow-up contact for identification of the efficacy and safety variables, defined as the first occurrence of bleeding (efficacy variable) and all-cause death, myocardial infarction, stent thrombosis, or stroke (safety variables).

7. SAFETY

The Principal Investigator at each participating study site is responsible for ensuring that all staff involved in the study is familiar with the content of this section.

7.1 Definition of adverse events

An adverse event is the development of an undesirable medical condition or the deterioration of a pre-existing medical condition following or during exposure to a pharmaceutical product, whether or not considered causally related to the product. An undesirable medical condition can be symptoms (e.g., nausea, chest pain), signs (e.g., tachycardia, enlarged liver) or the

abnormal results of an investigation (e.g., laboratory findings, electrocardiogram). In clinical studies, an AE can include an undesirable medical condition occurring at any time, including run-in or washout periods, even if no study treatment has been administered.

The term AE is used to include both serious and non-serious AEs.

7.2 Definitions of serious adverse event

A serious adverse event is an AE occurring during any study phase (i.e., run-in, treatment, wash-out, follow-up), that fulfills one or more of the following criteria:

- Results in death
- Is immediately life-threatening
- Requires in-patient hospitalization or prolongation of existing hospitalization
- Results in persistent or significant disability/incapacity or substantial disruption of the ability to conduct normal life functions
- Results in a congenital abnormality or birth defect
- Is an important medical event that may jeopardize the subject or may require medical intervention to prevent one of the outcomes listed above.

The severity and causality of SAEs (their relationship to all study treatments and/or procedures) will be assessed by the investigator(s) and communicated to the ARC.

7.2.1 Definition of suspected unexpected serious adverse reactions (SUSARs)

A SUSAR is a Suspected Unexpected Serious Adverse Reaction. To qualify as a SUSAR, the event must be:

- Serious
- Undesirable reaction to medicinal product
- Unexpected - NOT listed as a potential risk or reaction to the product as outlined in the protocol, informed consent document or literature.

7.3 Recording of adverse events or serious adverse events

7.3.1 Time period for collection of adverse events

All AEs related to bleeding and SAEs should be collected from the time the subject signs the informed consent through study exit.

7.3.2 Follow-up of unresolved adverse events

For ALL SAEs the subject's course must be monitored until the event has subsided or, in a case of permanent impairment, until the event stabilizes and the overall clinical outcome has been ascertained.

7.3.3 Information to be collected for each AE/SAE

- Description of AE/SAE
- The dates when the AE/SAE started and stopped
- Whether the AE/SAE is serious or not
- Investigator causality rating against the investigational product
- Action taken with regard to investigational product
- Whether the AE/SAE caused subject's withdrawal from study
- Outcome

In addition, the following variables will be collected for SAEs:

- Date the study site research personnel became aware of SAE
- Date when decision was made for meeting SAE criteria
- Criteria met leading to classification as SAE
- Date of hospitalization (if applicable)
- Date of discharge (if applicable)
- Date of death (if applicable)
- Probable cause of death (if applicable)
- Autopsy performed (if applicable)

It is important to distinguish between serious and severe AEs. Severity is a measure of intensity whereas seriousness is defined by the criteria in Section 7.2. An AE of severe intensity need not necessarily be considered serious. For example, nausea that persists for several hours may be considered severe nausea, but not an SAE. On the other hand, a stroke that results in only a limited degree of disability may be considered a mild stroke but would be an SAE.

7.3.4 Adverse Events based on signs and symptoms

When collecting AEs, the recording of diagnoses (when possible) is preferred to recording a list of signs and symptoms. However, if a diagnosis is known and there are other signs or symptoms that are not generally part of the diagnosis, the diagnosis and each sign or symptom will be recorded separately.

7.3.5 Adverse Events based on examinations and tests

Deterioration as compared to baseline in laboratory values or vital signs should therefore only be reported as AEs if they fulfill any of the SAE criteria or are the reason for discontinuation of treatment with the investigational product.

If deterioration in a laboratory value/vital sign is associated with clinical signs and symptoms, the sign or symptom will be reported as an AE and the associated laboratory result/vital sign will be considered as additional information. Wherever possible the reporting investigator uses the clinical, rather than the laboratory term (e.g., anemia versus low hemoglobin value). In the absence of clinical signs or symptoms, clinically relevant deteriorations in non-mandated parameters should be reported as AE(s).

Any new or aggravated clinically relevant abnormal medical finding at a physical examination as compared with the baseline assessment will be reported as an AE.

7.3.6 Disease progression or pre-existing conditions

Disease progression can be considered as a worsening of a subject's condition attributable to the disease for which the investigational product is being studied. It may be an increase in the severity of the disease under study and/or increases in the symptoms of the disease. For example, continued angina should be considered as disease progression and not an AE. Planned hospitalization for a pre-existing condition without serious deterioration in health, is not considered a serious adverse event.

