Randomized Medications – subject self-reporting of compliance to medications				X	X	X	X	X
Adverse Events / Serious Adverse Events	X	X	X	X	X	X	X	X

*If performed, as per standard of care. Subject may be asked to provide an additional blood sample (10cc) for lipid profile testing if not already performed per standard of care.

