11.1.4 Secondary Ischemic Endpoints

Time to first occurrence of:

- cardiovascular death, non-fatal myocardial infarction, ischemic stroke or clinically-driven revascularization
- cardiovascular death, non-fatal myocardial infarction or ischemic stroke
- definite or probable stent thrombosis
- cardiovascular death
- non-fatal myocardial infarction
- cardiovascular death, non-fatal myocardial infarction or definite or probable stent thrombosis
- ischemic stroke
- all-cause mortality

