15.2 Major Adverse Cardiovascular Events

Major adverse cardiovascular events (MACE) is the composite of cardiovascular death, non-fatal myocardial infarction, ischemic stroke, or clinically-driven revascularization. The definitions of the individual components of MACE are given below.

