15.2.5 Clinically driven revascularization

Clinically driven revascularization includes repeat PCI or CABG for recurrent or persistent symptomatic ischemia and can be defined according to the relationship to the index PCI (target lesion)(29):

- Target lesion revascularization, at the previously stented segment
- Non-target lesion, target vessel revascularization, of the previously treated vessel or its side branches AND
- Non-target vessel lesion revascularization, of a vessel other than the previously treated vessel

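### Could an elective repeat revascularisation for continued angina count in a secondary composite and yet go unreported?

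*Combined protocol and SAP*

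**What the plan says.** On the endpoint side, section 11.1.4 lists eight secondary ischemic endpoints. The first is time to "cardiovascular death, non-fatal myocardial infarction, ischemic stroke or clinically-driven revascularization". Section 15.2 gives the same composite a name: "Major adverse cardiovascular events (MACE) is the composite of cardiovascular death, non-fatal myocardial infarction, ischemic stroke, or clinically-driven revascularization". Section 15.2.5 supplies the definition: "Clinically driven revascularization includes repeat PCI or CABG for recurrent or persistent symptomatic ischemia". It does not require the procedure to be urgent or unplanned.

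On the collection side, section 6.3 has sites identify at follow-up the variables "defined as the first occurrence of bleeding (efficacy variable) and all-cause death, myocardial infarction, stent thrombosis, or stroke (safety variables"; revascularisation is not among them. Section 7.3.1 states that "All AEs related to bleeding and SAEs should be collected" from consent to study exit. Section 7.3.6 then says that "continued angina should be considered as disease progression and not an AE", and that "Planned hospitalization for a pre-existing condition without serious deterioration in health, is not considered a serious adverse event". In the schedule in 6.2, the row "Adverse Events / Serious Adverse Events" is ticked at all eight time points, four of them after randomisation (4, 9, 15 and 18 months). Procedure Information is ticked only at enrollment.

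**The concern.** The indication that makes a procedure count as an endpoint in 15.2.5 overlaps with the condition that 7.3.6 takes out of AE reporting. If an elective PCI for persisting angina is neither an AE nor an SAE, the AE/SAE row in the schedule does not oblige a site to enter it, and 6.3 does not ask for it separately. The omission from 6.3 cannot be put down to that section covering primary endpoints only, because it names stent thrombosis, which is a secondary endpoint.

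What would be at stake is the completeness of one secondary composite. Sites that read 7.3.6 differently would report differently, and an analyst cannot restore an event that was never entered.

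**Working it through.** The plan attaches no event rate, power, margin or alpha to this composite, so there is no stated figure to reproduce. The check traces one hypothetical event through the protocol: a planned repeat PCI after randomisation for persisting angina, with no serious deterioration.

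1. **Does it count?** Yes, under 15.2.5, and so under the first endpoint in 11.1.4.
2. **Is it named among the collected variables?** Not in 6.3, and not in the prompts of 6.2.3 and 6.2.4. Those prompts are introduced as examples, however. They also omit stent thrombosis, which 6.3 does require, so they are not a complete list of what sites record.
3. **Is it an AE or SAE?** Under 7.2 an SAE must first be an AE. Under 7.3.6 continued angina is not one, and the planned admission is not serious. Against this, 7.1 counts deterioration of a pre-existing condition as an AE, and angina that recurs after a successful PCI is not obviously continued angina. The literal exemption therefore fits the persistent half of the 15.2.5 definition better than the recurrent half.
4. **Does another section bring it in?**
   - Section 5.8 requires the date and reason of every interruption or discontinuation of study medication in the EDC. It names balloon angioplasty, bare-metal stenting and surgery as reasons to interrupt, and revascularisation with a DES among its examples of adverse events. This reaches the event only if medication is changed.
   - Section 5.2.1 lists post-PCI revascularisation with a DES as an ischemic event that bars randomisation. It applies before the analysis window, but shows how the plan regards such a procedure.
   - The schedule records Angina Status at all four post-randomisation contacts, so the symptom behind the procedure is asked about.
   - Section 12.4 has the DSMB review adjudicated and non-adjudicated MACE and bleeding alongside the remaining SAEs. The phrasing places MACE among the SAEs, and by 15.2 MACE includes this component.
   - Section 10 promises coded forms with instructions. Those forms are not among the documents.
5. **What is left?** A planned repeat procedure, with study medication unchanged, at a site that treats it as exempt under 7.3.6, on a form that does not ask about it. The last condition cannot be checked here.

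**Reach.** One of eight secondary ischemic endpoints contains revascularisation. The primary bleeding endpoint (11.1.1) and the primary ischemic endpoint (11.1.3) do not, so the sample size of 8200 and the 1.6% margin are untouched.

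**Direction.** Write the composite hazard in arm g as a_g + r_g, where r_g is the revascularisation part and a_g the rest. If a fraction f of that part goes unrecorded in both arms, the observed hazard is a_g + (1 − f)·r_g. When the two parts have the same hazard ratio, the composite ratio is unchanged and only precision falls. Otherwise it moves towards the ratio for a_g. The documents give neither f nor r_g, so no size can be put on this.

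**A figure that does not help.** The exclusion in 4.2 of planned revascularisation within 90 days concerns procedures already planned at entry. It says nothing about capturing procedures planned later, so its overlap with the 365-day analysis window does not measure the gap.

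**The case for a change.** The strongest case for acting is that adjudication needs a reported event. Sections 12.4 and 15.2 show intent, but no sentence orders sites to enter every repeat revascularisation. The routes in 5.8 are partial: interruption after balloon angioplasty or a bare-metal stent is optional, and the DES example is confined to events felt to be related to study medication. With approximately 100 sites, uneven reading of 7.3.6 is plausible, and the remedy would be a line or two of wording.

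Two parts of this stand. The wording of 6.3 is incomplete against 11.1.4, and uncollected events cannot be recovered later. What does not follow is that events would be lost. Section 7.3.6 is a safety-reporting rule. Read just as literally, its description of disease progression could also take in a myocardial infarction, which 6.3 plainly wants collected. Endpoint collection therefore does not hang on AE status. A trial that specifies this component as an endpoint, defines it and adjudicates the composite has to build a field for it, and the form is the natural place for that.

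**Conclusion.** The gap in wording is real, but it is missing detail that the trial team must fill to produce an endpoint it has already specified. No change to the plan is needed. Naming the component in 6.3 would be tidier, but no planned analysis would alter.

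The reach is one component of one of eight secondary ischemic endpoints, with no effect on either primary analysis. The number of events at risk cannot be derived from the documents. Under the double-blind design in 5.4.1 any under-reporting should be similar in both arms.

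The conclusion rests on two assumptions: that the unseen case report form asks about repeat revascularisation, as the MACE review in 12.4 implies, and that sites remain blinded when they decide what to report. If the form did not ask, the cost would be some loss of events and precision in this single composite.

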7.3.7 Reporting of adverse events

AEs must be reported to the sponsor within 7 business days of the study site research personnel's knowledge of the event via the EDC.

SAEs must be reported to the sponsor immediately, but no later than 24 hours, of the study site research personnel's knowledge of the event via the EDC.

The ARC Safety Monitor will review all submitted SAEs for qualification as a Suspected Unexpected Serious Adverse Reactions (SUSARs). The ARC will further report SAEs determined to qualify as SUSARs to the local regulatory body (IRB/EC).

The ARC Safety Monitor will voluntarily inform the FDA, via a MedWatch/AdEERs form, and EudraVigilance, of any serious adverse events which qualify as SUSARs in accordance with reporting requirements.

A copy of the MedWatch/AdEERs report will be faxed or scanned and sent to the Principal Investigator of the applicable site for reporting according to the site's local regulatory body's reporting requirements.

8. ETHICAL AND REGULATORY REQUIREMENTS

8.1 Ethical conduct of the study

The trial will be conducted in compliance with the protocol, Good Clinical Practice guidelines, and World Medical Association Declaration of Helsinki: Ethical Principles for Medical Research Involving Human Subjects as well as local regulations, and applicable regional regulatory requirements.

The clinical investigation shall not begin until the required approvals/favorable opinions from the respective regulatory authority and ethics committee have been obtained. Any additional requirements imposed by the respective regulatory authority and/or ethics committee will also be followed, where specified.

8.2 Ethics and regulatory review

Institutional Review Board (IRB) or Ethics Committee (EC) approval for the protocol, informed consent form and other trial related documents will be obtained by the Principal Investigator at each investigational site prior to participation in this trial. The approval letter must be signed by the IRB/EC chairperson or authorized representative prior to the start of this trial and a copy must be provided to the ARC. In addition, the Investigator or designee will provide the ARC with all required documentation necessary for initial and ongoing trial approval at their site.

In accordance with the investigational site IRB/EC requirements, the Investigator will

- (a) advise the IRB/EC of the progress of this trial on a regular basis until trial completion;
- (b) obtain written IRB/EC approval at predetermined time points to continue the trial; and
- (c) submit any amendments to the protocol as well as associated informed consent form changes and obtain written IRB/EC approval obtained prior to implementation.

8.3 Informed consent

All subjects must provide written informed consent in accordance with the site's IRB/EC, using an IRB/EC-approved informed consent form. All subjects are to be fully informed and trial conduct must be in accordance to the World Medical Association Declaration of Helsinki: Ethical Principles for Medical Research Involving Human Subjects.

Protocol-specific procedures or alterations of patient care must not be performed until the prospective subject has provided a signed informed consent. The informed consent will be in the prospective subject's native language and will contain non-technical language to describe the investigational procedures. The informed consent form should also include a clause that

ensures important new information will be provided to the subject throughout the clinical investigation.

After a review of the prospective subject's medical records to determine general eligibility, the investigator or authorized designee who has been trained on the protocol, will approach the prospective subject to explain the purpose and scope of the clinical trial, prospective risks, and benefits of participation. The prospective subject must be given the opportunity to ask questions about the trial and must be given sufficient time to decide to participate in the trial or not. Additional information requested by the prospective subject should be provided. Any coercion or undue improper influence on the prospective subject is to be avoided.

If the prospective subject agrees to participate, the informed consent form must be signed and personally dated by the prospective subject. The investigator or an authorized member of the research team who has witnessed the prospective subject's signature must also sign and date the informed consent, prior to enrollment of the prospective subject. A copy of the completed informed consent form must be provided to the subject. Local IRB/EC regulations regarding obtaining informed consent must be followed. The subject's medical record should have a notation regarding the signing of the informed consent.

The subject is to be made aware that their participation in the trial is voluntary, their legal rights will not be waived, and that they may withdraw from the trial at any time, without giving specific reason for doing so. The subject must also be informed that withdrawal from the trial will not affect their future treatment.

The investigator is responsible for the achievement of written consent from the prospective subject before they are included in the trial. All subjects must provide informed consent in accordance with the local IRB/EC requirements, using an IRB/EC-approved informed consent form.

8.4 Changes to the protocol and informed consent form

If the protocol or informed consent form (ICF) needs an amendment, the ARC is required to submit such amendment to the Regulatory Agencies and/or other regulating body in each participating country for approval. Approved protocol or ICF amendments will be provided to the Investigators by the ARC prior to implementing the amendment.

For administrative changes, the Principal Investigator is responsible for notifying the IRB/EC of the protocol or ICF amendment. For changes involving subject care or safety, the Principal Investigator is responsible for obtaining IRB/EC approval of the protocol or ICF amendment according to the instructions provided by the ARC with the protocol or ICF amendment.

Acknowledgement/approval by the IRB/EC of the protocol or ICF amendment must be documented in writing prior to implementation of the protocol or ICF amendment. Copies of this documentation must also be provided to the ARC.

8.5 Deviations from protocol

8.5.1 Compliance to protocol

No investigative procedures other than those defined in this clinical investigational plan will be undertaken on the enrolled subjects without the written agreement of the IRB/EC and ARC. It is the Investigator's responsibility to ensure that there are no deviations from the clinical investigational plan and full compliance with all established procedures of the IRB/EC is maintained. The Investigator will not deviate from the clinical investigational plan for any reason except in cases of medical emergencies, when the deviation is necessary to protect the life or physical well-being of the subject.

8.5.2 Procedures for recording, reporting, and analyzing protocol deviations

A deviation is an instance(s) of failure to follow, intentionally or unintentionally, the requirements of the protocol. All deviations must be reported to the ARC. The occurrence of clinical investigational plan deviations will be monitored by the ARC or designee. It is the Investigator's responsibility to inform their IRB/EC of clinical investigational plan deviations in accordance with their specific IRB/EC reporting policies and procedures.

In the event that an investigative site does not comply with the Investigator Agreement or clinical investigational plan, the ARC will notify the Investigator of the site's non-compliance. Continued non-compliance may result in further escalation in accordance with the ARC's standard procedures.

